9.1. Estimands and Statistical Hypotheses

The primary objective of assessing noninferiority of the 2-dose regimen to the 3-dose regimen will be evaluated at 1 month after the last vaccination for each *C difficile* toxin A— or toxin B—specific neutralizing antibody. The evaluable immunogenicity population will be used for the hypothesis testing to assess the primary immunogenicity objective.

The 2 null hypotheses (H_0) for noninferiority are:

$$H_{01}$$
: $ln(\mu_2) - ln(\mu_3) \le -ln(1.5)$

Where, for each of toxin A– and toxin B–specific neutralizing antibody, $ln(\mu_2)$ and $ln(\mu_3)$ are the means of the natural logarithm-transformed concentrations from participants receiving the 2-dose regimen and the 3-dose regimen, respectively, measured 1 month after the last vaccination with the *C difficile* vaccine (Month 7). The analysis of covariance (adjusted for baseline concentration) will be used to test these null hypotheses, and corresponding 95% CIs will be provided.

and

$$H_{02}$$
: $P_2 - P_3 \le -10\%$

Where, for each of toxin A– and toxin B–specific neutralizing antibody, P_2 and P_3 are the seroresponse rates achieved by participants receiving the 2-dose regimen and the 3-dose regimen respectively, measured 1 month after the last vaccination with C difficile vaccine (Month 7). A participant achieves seroresponse if the participant has a 4-fold rise after vaccination.

If the lower limit of the 2-sided 95% CI for the GMC ratio (2-dose/3-dose) is > 0.67 and the lower limit of the 2-sided 95% CI for the difference between the regimens (2-dose minus 3-dose) in the percentage of participants achieving seroresponse is > -10% for both toxin A-and toxin B-specific neutralizing antibodies, 1 month after the last vaccination, the primary objective of establishing noninferiority of the 2-dose regimen to the 3-dose regimen is met.

If this primary immunogenicity objective is met, the same null hypotheses for the secondary immunogenicity objective will be evaluated 6 months after the last vaccination.

Estimands

Endpoint	Estimands
Primary	Immunogenicity:
	For each of toxin A– and toxin B–specific neutralizing antibody levels: Adjusted GMC ratio, estimated by the ratio of the adjusted GMC at Month 7 (adjusted for baseline concentration), for the 2-dose regimen to the adjusted GMC for the 3-dose regimen, in participants receiving C difficile vaccine and in compliance with the key protocol criteria (evaluable participants).

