9.2. Sample Size Determination

In order to meet the immunogenicity primary objective, the study sample size estimate is based upon the evaluation of the primary immunogenicity objective of the study to demonstrate that the immune responses induced by 2 doses of C difficile vaccine (administered in a 0- and 6-month regimen) are noninferior to the immune responses induced by 3 doses of C difficile vaccine (administered in a 0-, 1-, and 6-month regimen) – by evaluating the toxin A- and toxin B- specific neutralizing antibody in terms of GMC ratios and difference in the percentage of participants achieving seroresponse, 1 month after the last investigational product administration. Regimen comparisons will be based on two primary endpoints: (1) the adjusted GMC ratio (adjusted for baseline antibody concentration); and (2) the difference in the percentage of participants achieving seroresponse, 1 month after the last vaccination (Month 7), and the corresponding 95% CIs. The noninferiority of a 2-dose regimen to a 3-dose regimen at 1 month after the last vaccine dose will be evaluated using a 1.5-fold NI margin for the adjusted GMC ratio and a 10% NI margin for the difference in seroresponse rates. Pfizer has developed a new assay which will be used for serology testing in this study. The new assay was used to test Study B5091009 retrospectively, and the standard deviation was evaluated. Therefore, the computation of the sample size for the GMC ratio is based on (1) the standard deviations (0.794 for toxin A and 1.059 for toxin B) from Study B5091009 data tested by the new assay and (2) an assumption that the true mean difference between the 2 regimens for both toxin A- and toxin B-specific neutralizing antibody levels is no more than 0.2 on the logarithmic scale. Similarly, the reference for the computation of the sample size for the difference in seroresponse rate is based on the percentage of seroresponse (4-fold rise from baseline) observed from Study B5091009, and an assumption that the true seroresponse rate for the 2-dose regimen is no more than 7% lower than the ones from the 3-dose regimen. A sample size of 784 evaluable participants per regimen will provide a power of 96.91% to declare the noninferiority of a 2-dose regimen to a 3-dose regimen for both toxin A and toxin B in terms of the GMC ratio, 1 month after the last dose (see Table 6). The sample size will also provide a power of 93.43% to declare the noninferiority of a 2-dose regimen to a 3-dose regimen for both toxin A and toxin B in terms of the difference of percentage of participants achieving seroresponse, 1 month after the last dose (see Table 7). Thus, the overall power to meet the study primary immunogenicity objective is 90.5%.

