
Table 6. Power Analysis (Primary Immunogenicity Objective: Noninferiority for GMC ratio)

Criteria	Neutralizing Antibody	Standard Deviation (Log Value) ^a	Assume Observed Log GMC Difference	Number of Evaluable Participants per Regimen	Power ^b	Power to Meet NI for Both Toxins at 1 Month After Dose 3
Lower limit of	Toxin A	0.794	0.2	784	99.92%	96.91%
95% CI for GMC ratio (2 doses/3 doses) > 0.67	Toxin B	1.059	0.2	784	96.99%	

Abbreviations: GMC = geometric mean concentration; NI = noninferiority.

Table 7. Power Analysis (Primary Immunogenicity Objective: Noninferiority for Difference in Seroresponse)

Criteria	Neutralizing Antibody	Observed % of seroresponse from 3-dose group ^a	Assume % of seroresponse from 2-dose group	Number of Evaluable Participants per Regimen	Power ^b	Power to Meet NI for Both Toxins at 1 Month After Dose 3
Lower limit of 95% CI for difference in seroresponse rate (2 doses minus 3 doses) > -10%	Toxin A	91.8%	86%	784	96.14%	93.43%
	Toxin B	93.7%	86%	784	97.18%	

Note: Seroresponse = Participant achieves at least a 4-fold rise after the last vaccination

If the primary immunogenicity objective is met, the secondary immunogenicity objective will be evaluated by the same criteria. For the secondary immunogenicity objective, if the noninferiority criterion for the GMC ratio is met at Month 12, then the evaluation of the difference between regimens in seroresponse at Month 12 will follow.

A sufficient number of participants will be screened to achieve 1960 participants randomly assigned to investigational product and 1568 evaluable participants (assuming a maximum study nonevaluable rate of 20% and a randomization ratio of 1:1), for an estimated total of 784 evaluable participants per vaccine group in order to meet the primary immunogenicity objectives.

a. Reference Study B5091009 tested by new assay, 1 month after Dose 3.

b. At 0.05 alpha level (2-sided).

a. Reference Study B5091009.

b. At 0.05 alpha level (2-sided).

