2.2.2. Number of Participants

In order to meet the immunogenicity primary objective, the study sample size estimate is based upon the evaluation of noninferiority of a 2-dose regimen to a 3-dose regimen with respect to toxin A— and toxin B—specific neutralizing antibodies.

Regimen comparisons will be based on 2 primary endpoints assessed 1 month after the last dose (Month 7):

- 1. The GMC ratios adjusted by the baseline antibody level and corresponding 95% confidence intervals (CIs).
- 2. The difference in percentage of participants achieving seroresponse and the corresponding 95% CIs.

The noninferiority of a 2-dose regimen to a 3-dose regimen at 1 month after the last dose will be evaluated using a 1.5-fold noninferiority margin for the adjusted GMC ratio and a 10% noninferiority margin for the difference of seroresponse rate as noninferiority criteria.

Pfizer has developed a new assay that will be used for serology testing in this study. The new assay was used to test Study B5091009 samples retrospectively, and the standard deviation was evaluated. Therefore, the computation of the sample size for the GMC ratio is based on (1) the standard deviations (0.794 for toxin A and 1.059 for toxin B) from Study B5091009 samples tested by the new assay and (2) an assumption that the true mean difference between the 2 regimens for both toxin A- and toxin B-specific neutralizing antibody levels is no more than 0.2 on the logarithmic scale. Similarly, the reference for the computation of the sample size for the difference in seroresponse rate is based on the percentage of seroresponse (4-fold rise from baseline) observed from Study B5091009, and an assumption that the true seroresponse rate for the 2-dose regimen is no more than 3% lower than the rate for the 3-dose regimen. A sample size of 784 evaluable participants per regimen will provide a power of 96.91% to declare the noninferiority of a 2-dose regimen to a 3-dose regimen for both toxin A and toxin B in terms of the GMC ratio, 1 month after the last dose (Table 3). The sample size will also provide a power of 93.64% to declare the noninferiority of a 2-dose regimen to a 3-dose regimen for both toxin A and toxin B in terms of the difference of percentage of participants achieving seroresponse, 1 month after the last dose (Table 4). Thus, the overall power to meet the study primary immunogenicity objective is 90.7%.

Table 3. Power Analysis (Primary Immunogenicity Objective: Noninferiority for GMC Ratio)

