5.1. Hypotheses and Decision Rules

5.1.1. Analysis of the Primary Immunogenicity Endpoint

The primary objective of assessing noninferiority of the 2-dose regimen to the 3-dose regimen will be tested for each of *C difficile* toxin A– or toxin B–specific neutralizing antibody levels determined at 1 month after the last vaccination using participants in the EI7 population.

The 2 null hypotheses (H_0) for noninferiority are:

$$H_{01}: \ln(\mu_2) - \ln(\mu_3) \le -\ln(1.5)$$

where $ln(\mu_2)$ and $ln(\mu_3)$ are the means of the natural logarithm-transformed C difficile toxin A— or toxin B—specific neutralizing antibody levels from participants receiving the C difficile vaccine 2-dose regimen and 3-dose regimen, respectively, measured 1 month after the last vaccination (Month 7) of the vaccine regimen. Baseline adjusted GMC ratios, along with 95% CIs, will be computed for each of toxin A— or toxin B—specific neutralizing antibody levels and will be used to test the null hypothesis.

and

 H_{02} : $P_2 - P_3 \le -10\%$

where P₂ and P₃ are the percentage of participants with a seroresponse in *C difficile* toxin A– or toxin B–specific neutralizing antibody levels from participants receiving the *C difficile* vaccine 2-dose regimen and 3-dose regimen, respectively, measured 1 month after the last vaccination (Month 7) of the vaccine regimen. A participant achieves seroresponse if the participant has at least a 4-fold rise in the respective antibody levels for the proposed analysis time point relative to the levels from baseline. Baseline concentration is defined as the antibody concentration results from the blood drawn before vaccine Dose 1. The difference in percentage of participants achieving seroresponse and the associated 95% CIs will be calculated using the Miettinen and Nurminen method.

The primary immunogenicity objective of the noninferiority of the 2-dose regimen to the 3-dose regimen will be achieved if the lower limit of the 2-sided 95% CI for the GMC ratio (2-dose/3-dose) is > 0.67 and the lower limit of the 2-sided 95% CI for the difference between the regimens (2-dose) in the percentage of participants achieving seroresponse is > -10% for both toxin A— and toxin B—specific neutralizing antibody levels assessed 1 month after the last vaccination.

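### The GMC success threshold of 0.67 is 1/1.5 rounded up, so the printed rule is slightly stricter than H01, the 1.5-fold margin and the tabulated power

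*Protocol*

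**What the plan says.** H01, in Protocol 9.1 and again in SAP 5.1.1, places the log-scale difference (2-dose minus 3-dose) at or below -ln(1.5). The sample-size text matches it: Protocol 9.2 evaluates noninferiority "using a 1.5-fold NI margin for the adjusted GMC ratio and a 10% NI margin" for seroresponse, and SAP 2.2.2 also names a 1.5-fold margin.

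The rule that decides the trial uses another number. In Protocol 9.1 it begins "If the lower limit of the 2-sided 95% CI for the GMC ratio (2-dose/3-dose) is > 0.67". SAP 5.1.1 declares the primary objective achieved if "the lower limit of the 2-sided 95% CI for the GMC ratio (2-dose/3-dose) is > 0.67", together with the seroresponse criterion, for both toxins. The value 0.67 also appears in the protocol synopsis and in Protocol 9.4.1.1 for Month 7, and in Protocol 9.4.1.2 and SAP 5.1.2 for Month 12.

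The GMC power tables (Protocol Table 6, SAP Table 3) print the criterion as "95% CI for GMC ratio (2 doses/3 doses) > 0.67". Beside it they give powers of 99.92% (toxin A), 96.99% (toxin B) and 96.91% (both). Overall power is stated as 90.5% in the protocol (synopsis and 9.2) and 90.7% in SAP 2.2.2.

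**The concern.** The ratio 1/1.5 is 0.66667, not 0.67. On the log scale the two values are -0.40547 and -0.40048. A lower limit above 0.6667 but not above 0.67 rejects H01 as written and still fails the success rule.

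This is the primary decision threshold. It must be met for both toxins, it gates the Month 12 objective, and it is used again there. Two things are at stake. The first is whether the tabulated power belongs to the rule printed beside it. The second is whether someone holding a borderline result could later argue over whether 0.67 was meant literally or as shorthand for 1/1.5.

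**Working it through.** **Inputs** (Protocol 9.2 and Table 6; the same in SAP 2.2.2 and Table 3)
- 784 evaluable participants per regimen
- SD on the log scale: 0.794 (toxin A), 1.059 (toxin B)
- True log difference: 0.2, with the 2-dose regimen lower
- Alpha 0.05 two-sided, so 0.025 one-sided for noninferiority
- Joint seroresponse power: 93.43% (protocol), 93.64% (SAP)

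**Formula.** SE = SD × √(2/784). The noncentrality is (margin − 0.2)/SE. Power is the probability that a noncentral t variable with 1566 df exceeds 1.9615.
- SE, toxin A: 0.794 × 0.050508 = 0.04010
- SE, toxin B: 1.059 × 0.050508 = 0.05349

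**Step 1: the plan's own figures, margin ln(1.5) = 0.40547**
- Toxin A: 0.20547/0.04010 gives noncentrality 5.123 and power 99.92%
- Toxin B: 0.20547/0.05349 gives 3.841 and 96.99%
- Both: 0.99921 × 0.96988 = 96.91%
- Overall: 96.91% × 93.43% = 90.5%; 96.91% × 93.64% = 90.7%

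Every stated figure is reproduced to the printed decimals. The power was therefore computed at 1/1.5, on the natural-log scale.

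**Step 2: the printed rule, margin −ln(0.67) = 0.40048**
- Toxin A: 0.20048/0.04010 gives 4.999 and 99.88%
- Toxin B: 0.20048/0.05349 gives 3.748 and 96.29%
- Both: 0.99880 × 0.96294 = 96.18%
- Overall: 96.18% × 93.43% = 89.9%; 96.18% × 93.64% = 90.1%

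| Power | Stated | At 1/1.5 | At 0.67 |
|---|---|---|---|
| Toxin A | 99.92% | 99.92% | 99.88% |
| Toxin B | 96.99% | 96.99% | 96.29% |
| Both toxins | 96.91% | 96.91% | 96.18% |
| Overall, protocol | 90.5% | 90.5% | 89.9% |
| Overall, SAP | 90.7% | 90.7% | 90.1% |

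**Step 3: chance of a lower limit in the gap.** This is the difference between the two powers (normal approximation).
- Toxin A: 99.922% − 99.881% = 0.04%
- Toxin B: 97.004% − 96.312% = 0.69%

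**Step 4: direction of the error.** When the true ratio is exactly 1/1.5, passing > 0.67 needs a further ln(1.5) + ln(0.67) = 0.00499 on the log scale. One-sided type I error (normal approximation) is:
- Toxin A: 1 − Φ(1.960 + 0.00499/0.04010) = 0.0186
- Toxin B: 1 − Φ(1.960 + 0.00499/0.05349) = 0.0200

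Both are below 0.025. The smallest observed ratio that passes, exp(ln(threshold) + 1.96 × SE), moves from 0.721 to 0.725 for toxin A and from 0.740 to 0.744 for toxin B.

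**The case against.** The strongest reply is that no calculation in the plan is wrong and 0.67 is plainly 1/1.5 to two decimals. That is very probably so, and it is why the point is minor. But neither document says it, and the tables attach two-decimal powers to a criterion that does not produce them.

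A reader might infer more than the documents support, in three ways.
- **That hypothesis, threshold and power all disagree.** They do not. H01, the 1.5-fold margin and the powers agree exactly; the threshold alone is out of line.
- **That a lower limit in the gap yields two contradictory primary conclusions.** Success is defined only by the > 0.67 rule with the seroresponse criterion, and nowhere does rejecting H01 alone meet the objective. A limit in the gap has one prespecified outcome: objective not met. Any result that passes > 0.67 also rejects H01, so no false claim follows.
- **That the trial drops below a required 90% power.** Neither document sets a 90% target. The 89.9% also uses the protocol's seroresponse power, which SAP Version 2 recalculated after changing how values below the LLOQ are handled.

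It is also fair that the figures at 0.67 are planning approximations. The product treats criteria measured in the same participants as independent. Using the tabulated seroresponse powers, the bounds under any dependence are:
- Protocol: lower 99.88% + 96.29% + 96.14% + 97.18% − 300% = 89.5%; upper 96.1%, the smallest of the four.
- SAP: lower 99.88% + 96.29% + 93.93% + 99.7% − 300% = 89.8%; upper 93.9%.

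The stated 90.5% and 90.7% lie inside these ranges. If the planning SDs are not baseline-adjusted, the ANCOVA could also recover the loss. An assumed baseline correlation of 0.22 would cut toxin B's SD to 1.059 × √(1 − 0.22²) = 1.033 and restore about 96.99% at 0.67. The documents give no correlation. These points limit how much weight the 0.7-point difference can bear. They do not make the printed criterion the one that was powered.

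**Conclusion.** The point holds as a minor inconsistency. The GMC success threshold is 1/1.5 rounded up, and it is slightly stricter than the margin in H01, the stated 1.5-fold margin and the margin behind the power tables. With the plan's own inputs and its product method, the literal rule costs 0.04 points of power for toxin A, 0.70 for toxin B, 0.73 for both toxins and about 0.7 overall. The error is conservative and does not threaten type I error control.

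These sizes rest on the planning SDs, a true log difference of 0.2, no gain from baseline adjustment, and independence of the criteria. The mismatch between the printed criterion and the margin behind the GMC powers needs none of the last three assumptions changed to be seen: at the plan's own settings, only ln(1.5) gives the printed figures.

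**What to change.** Before the sponsor's study team is unblinded at the Month 7 snapshot (Protocol 6.3.3), state the rule as a lower limit greater than 1/1.5, unrounded, at every occurrence:
- Protocol: synopsis, 9.1, Table 6, 9.4.1.1 and 9.4.1.2 (Month 12)
- SAP: Table 3, 5.1.1 and 5.1.2 (Month 12)

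H01, the 1.5-fold wording and all stated powers then stay as they are, and the rule delivers the power printed beside it. This relaxes the literal threshold by 0.0033 on the ratio scale (0.67 − 0.6667), to the margin the plan already names. It should therefore be dated before unblinding and made in both documents.

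If > 0.67 is kept instead, these must all be restated together:
- H01 in Protocol 9.1 and SAP 5.1.1, written with ln(0.67)
- the 1.5-fold wording in Protocol 9.2 and SAP 2.2.2
- Protocol Table 6, SAP Table 3 and the joint GMC power in the text beside them: 99.88%, 96.29% and 96.18%
- overall power: 89.9% in the protocol synopsis and 9.2, and 90.1% in SAP 2.2.2

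Changing only some of these would leave a new mismatch. Either route is wording only, with no change to sample size or analysis method.

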9.2. Sample Size Determination

In order to meet the immunogenicity primary objective, the study sample size estimate is based upon the evaluation of the primary immunogenicity objective of the study to demonstrate that the immune responses induced by 2 doses of C difficile vaccine (administered in a 0- and 6-month regimen) are noninferior to the immune responses induced by 3 doses of C difficile vaccine (administered in a 0-, 1-, and 6-month regimen) – by evaluating the toxin A- and toxin B- specific neutralizing antibody in terms of GMC ratios and difference in the percentage of participants achieving seroresponse, 1 month after the last investigational product administration. Regimen comparisons will be based on two primary endpoints: (1) the adjusted GMC ratio (adjusted for baseline antibody concentration); and (2) the difference in the percentage of participants achieving seroresponse, 1 month after the last vaccination (Month 7), and the corresponding 95% CIs. The noninferiority of a 2-dose regimen to a 3-dose regimen at 1 month after the last vaccine dose will be evaluated using a 1.5-fold NI margin for the adjusted GMC ratio and a 10% NI margin for the difference in seroresponse rates. Pfizer has developed a new assay which will be used for serology testing in this study. The new assay was used to test Study B5091009 retrospectively, and the standard deviation was evaluated. Therefore, the computation of the sample size for the GMC ratio is based on (1) the standard deviations (0.794 for toxin A and 1.059 for toxin B) from Study B5091009 data tested by the new assay and (2) an assumption that the true mean difference between the 2 regimens for both toxin A- and toxin B-specific neutralizing antibody levels is no more than 0.2 on the logarithmic scale. Similarly, the reference for the computation of the sample size for the difference in seroresponse rate is based on the percentage of seroresponse (4-fold rise from baseline) observed from Study B5091009, and an assumption that the true seroresponse rate for the 2-dose regimen is no more than 7% lower than the ones from the 3-dose regimen. A sample size of 784 evaluable participants per regimen will provide a power of 96.91% to declare the noninferiority of a 2-dose regimen to a 3-dose regimen for both toxin A and toxin B in terms of the GMC ratio, 1 month after the last dose (see Table 6). The sample size will also provide a power of 93.43% to declare the noninferiority of a 2-dose regimen to a 3-dose regimen for both toxin A and toxin B in terms of the difference of percentage of participants achieving seroresponse, 1 month after the last dose (see Table 7). Thus, the overall power to meet the study primary immunogenicity objective is 90.5%.

Table 6. Power Analysis (Primary Immunogenicity Objective: Noninferiority for GMC ratio)

Criteria	Neutralizing Antibody	Standard Deviation (Log Value) ^a	Assume Observed Log GMC Difference	Number of Evaluable Participants per Regimen	Power ^b	Power to Meet NI for Both Toxins at 1 Month After Dose 3
Lower limit of	Toxin A	0.794	0.2	784	99.92%	96.91%
95% CI for GMC ratio (2 doses/3 doses) > 0.67	Toxin B	1.059	0.2	784	96.99%	

Abbreviations: GMC = geometric mean concentration; NI = noninferiority.

Table 7. Power Analysis (Primary Immunogenicity Objective: Noninferiority for Difference in Seroresponse)

Criteria	Neutralizing Antibody	Observed % of seroresponse from 3-dose group ^a	Assume % of seroresponse from 2-dose group	Number of Evaluable Participants per Regimen	Power ^b	Power to Meet NI for Both Toxins at 1 Month After Dose 3
Lower limit of 95% CI for difference in seroresponse rate (2 doses minus 3 doses) > -10%	Toxin A	91.8%	86%	784	96.14%	93.43%
	Toxin B	93.7%	86%	784	97.18%	

Note: Seroresponse = Participant achieves at least a 4-fold rise after the last vaccination

If the primary immunogenicity objective is met, the secondary immunogenicity objective will be evaluated by the same criteria. For the secondary immunogenicity objective, if the noninferiority criterion for the GMC ratio is met at Month 12, then the evaluation of the difference between regimens in seroresponse at Month 12 will follow.

A sufficient number of participants will be screened to achieve 1960 participants randomly assigned to investigational product and 1568 evaluable participants (assuming a maximum study nonevaluable rate of 20% and a randomization ratio of 1:1), for an estimated total of 784 evaluable participants per vaccine group in order to meet the primary immunogenicity objectives.

a. Reference Study B5091009 tested by new assay, 1 month after Dose 3.

b. At 0.05 alpha level (2-sided).

a. Reference Study B5091009.

b. At 0.05 alpha level (2-sided).

